### 9 STATISTICAL CONSIDERATIONS

#### 9.1 STATISTICAL HYPOTHESES

- Primary Endpoint:  
The primary objective is to determine the effectiveness of a peer support telephone intervention compared with usual care to reduce a composite of ED visits and hospitalizations among patients receiving in-center hemodialysis for ESKD. The null hypothesis is that the count of composite events at the end of the study period between intervention and usual care are the same. The alternative hypothesis is that the count of composite events at the end of the study period are different.
- Secondary Endpoint(s):
  - To determine the effectiveness of a peer support phone intervention compared to usual care to improve:
    - dialysis self-management including:
      - Dialysis treatment schedule adherence (mean minutes missed per month)
      - Inter-dialytic weight gain (IDWG) (mean monthly %)
    - nutritional status (serum albumin)
    - dialysis knowledge
    - dialysis self-management self-efficacy
    - social support (general and dialysis-specific)
    - coping skills
    - quality of life
    - communication with providers
- The null hypothesis is that the secondary endpoint values at the end of the study period between intervention and usual care are the same. The alternative hypothesis is that the secondary endpoint values at the end of the study period are different.
- Feasibility endpoint(s):
  - To determine the feasibility of a structured, multicomponent, multiple session peer mentor training program at two sites. There is no specified hypothesis.
  - To determine the acceptance of peer mentor phone intervention by patients. There is no specified hypothesis.

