**Table 4. Scientific Questions to be Addressed with the Trial**

Scientific question	Outcome(s)	Analysis
1. Does phone peer support improve outcomes at 18-months (*12 to 18-months)?	
 
Primary: composite endpoint count of ED visit and hospitalization events
 
Secondary: Various as listed above
 
	Poisson regression with two random intercepts. Random intercepts account for clusters by (1) mentor; (2) dialysis unit  See Section 9.4.2 (Primary); 9.4.3 (Secondary)
2. Is a peer mentor training program feasible?	
 
Attendance records
 
Pre- and Post-knowledge test scores
 
Satisfaction with training
 
Summative assessment
 
	Paired t-tests  Descriptive summaries and content analysis of qualitative data
3. Is a peer mentor training program accepted by patient receiving hemodialysis	
 
Satisfaction with intervention
 
Communication rating of mentors
 
	Descriptive  Content analysis of qualitative data

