## 9.2 SAMPLE SIZE DETERMINATION

For evaluation of the primary endpoint, estimates are based on local dialysis unit hospitalization events in the past 12 months. For the control group, we expect 0.27 events per month (100 prevalent patients and 27 composite events per month). With 73 patients per group (after 25% drop-out), our study has >80% power to detect 20% reduction (i.e. a reduction of 0.054 visits per person-month) at type 1 error level 0.05. We will recruit at least 100 patients per group over the course of the study.

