## 9.4 STATISTICAL ANALYSES

### 9.4.1 GENERAL APPROACH

Descriptive statistics will be used to provide for each variable: number of observations, mean, standard deviation, median, minimum and maximum for continuous variables; frequencies and proportions for categorical variables. Results will be reported in accordance with the extended CONSORT guidelines for pragmatic clinical trials using two-sided statistical tests and confidences intervals. For all analyses, the overall level of significance will be set at 0.05. All analyses will be adjusted for site. Adjustment variables will be pre-specified in the following sections. All analyses will be performed using SAS v9.4 (SAS Institute, Cary, NC), STATA (College Station, Tx), or R (currently 3.6.1; <https://cran.r-project.org/>).

Analyses of qualitative data will include content analysis, novel code generations as applicable, interpretation and descriptive reporting.

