#### 9.4.2 ANALYSIS OF THE PRIMARY ENDPOINT(S)

##### ED Visit and Hospitalization Count

Each month all enrolled patients will be evaluated for ED visit or hospitalization encounters by both self-report and medical record review. The events will be tabulated each month up to an 18-month period of follow-up. The rates of the composite event will be determined as event per patient-month and compared between the intervention and usual care group using Poisson regression with two random intercepts. In the regression model, the composite counts of ED visits and hospitalization during up to 18-months follow-up is the outcome variable and the intervention assignment of the mentees is the primary binary predictor. The log of follow-up time will be included as offset. The random intercepts will account for the correlation between mentees who share a common mentor as well as the correlation between mentees who are from a common dialysis facility (out of seven facilities). As a randomized controlled trial, we do not anticipate the need for covariate adjustment. However, if evaluation of patient characteristics by group identifies a failure of randomization and imbalance in key characteristics as an example including age, gender, comorbidity, race, or dialysis vintage they will be considered as adjustment variables in the analysis. We will control for type 1 error at 0.05. An exploratory analysis will consider the comparison between the groups but at 3-months of observation after the conclusion of the intervention delivery.

We will perform residual analysis for the mixed effects models. For mixed effects models, we will examine marginal residuals to check linearity and within-subjects covariance matrix and conditional residuals to check outliers as well as normality and homoscedasticity of the residual errors. In case Pearson residual analyses indicate overdispersion in the Poisson mixed effects model, we will perform quasi-Poisson model. We will use robust sandwich estimator in the presence of misspecification of the covariance matrix (i.e. random effects structure).

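### The primary model's mentor intercept has no stated coding for usual care; on the natural mentees-only reading, its arm coefficient does not test equal counts and leans toward the intervention

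*Combined protocol and SAP*

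**What the plan says.** Section 9.1 sets the primary hypothesis in terms of counts: "The null hypothesis is that the count of composite events at the end of the study period between intervention and usual care" are equal. Table 4 names the analysis as Poisson regression with two random intercepts: "Random intercepts account for clusters by (1) mentor; (2) dialysis unit". Section 9.4.2 repeats this, with a binary arm term and log follow-up time as offset, and explains the mentor term: "The random intercepts will account for the correlation between mentees who share a common mentor". It adds: "We will control for type 1 error at 0.05". Section 9.4.1 specifies "using two-sided statistical tests and confidences intervals" and adjustment of all analyses for site.

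The usual-care description in Section 6.1.1 gives that group written materials and its usual providers, with no mentor. Neither Section 9.4.2 nor Table 4 says which level of the mentor term, if any, a usual-care patient takes. No mentor variance is given. The primary model has no patient-level random effect, although the repeated-measures model in Section 9.4.3 has one. Section 9.4.2 names a quasi-Poisson model and a sandwich estimator as fallbacks after residual checks. It does not say whether the quasi-Poisson model keeps the mentor term.

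**The concern.** A random intercept on the log scale raises the mean rate of the patients it acts on by a factor exp(s²/2). If it acts in both arms, as the facility intercept does, the factor cancels from the rate ratio. If it acts in one arm only, it does not cancel, and the arm coefficient compares usual care with the median mentor instead of comparing mean counts. A test of zero is then not a test of the null in Section 9.1, and the reported rate ratio is displaced along with its p-value.

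A true difference between mentors is not needed. Mentees are paired with mentors on language, sex, age group and race (Section 6.1.1), so mentor groups can differ before any mentoring. With no patient-level term in the model, ordinary differences in event rate between patients also load onto the mentor term. At stake are the primary estimate and the 5% error rate that Section 9.4.2 promises.

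**Working it through.** **Inputs from the documents.** Control rate: "For the control group, we expect 0.27 events per month" per patient (Section 9.2). Evaluable patients: 73 per arm after 25% drop-out (9.2); enrolment 100 per arm. Follow-up: 12 to 18 months. Mentors: J = 17 (Section 5; the synopsis says 20). Two-sided 0.05.

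**Assumed.** Mentor SD s on the log scale and patient-level variance; the documents give neither. For scale, s = 0.3 means that a mentor one SD above the median has exp(0.3) = 1.35 times the median event rate; s = 0.5 means 1.65 times.

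**1. The plan's own figure.** Section 9.2 states: "our study has >80% power to detect 20% reduction". At 73 × 18 months, expected events are 0.27 × 1314 = 354.8 and 0.8 × 354.8 = 283.8. SE of the log rate ratio = sqrt(1/354.8 + 1/283.8) = 0.0796. |log 0.8| / SE = 0.2231 / 0.0796 = 2.80, so power is Φ(2.80 - 1.96) = 0.80. The figure reproduces, for plain Poisson counts with no clustering.

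**2. Mentees-only intercept.** The mean rate is exp(a) under usual care and exp(a + b + s²/2) for mentees. Equal means require b = -s²/2. Approximately, SE(b) = sqrt(2/E + s²/J), with E the expected events per arm. The false-positive rate for benefit is Φ(-1.96 + s²/(2·SE)), and for harm Φ(-1.96 - s²/(2·SE)).

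At s = 0.3 and E = 354.8: b = -0.045, SE = sqrt(0.00564 + 0.09/17) = 0.1046, shift 0.430. Benefit Φ(-1.530) = 6.3%; harm Φ(-2.390) = 0.8%.

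| s | Null rate ratio exp(-s²/2) | Benefit / harm | Share for benefit |
|---|---|---|---|
| 0.1 | 0.995 | 2.9% / 2.2% | 57% |
| 0.2 | 0.980 | 4.1% / 1.5% | 74% |
| 0.3 | 0.956 | 6.3% / 0.8% | 88% |
| 0.4 | 0.923 | 9.6% / 0.5% | 96% |
| 0.5 | 0.882 | 13.9% / 0.2% | 98% |

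Fitting the model by maximum likelihood to data simulated with equal means (1500 runs per setting, facility term omitted) agrees. At s = 0.3, mean b is -0.042 and rejections are 6.3% / 1.7% (73 × 18) and 6.0% / 1.1% (100 × 12). At s = 0.5, mean b is -0.124 to -0.127 and rejections are 13.7% / 0.5% and 13.9% / 0.9%. A separate 500-run simulation at 100 × 12 gave totals of 7.2% and 17.6%. With neither mentor nor patient variance there is no lean (2.2% / 2.4%; 2.5% / 1.7%).

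**3. Patient heterogeneity, no mentor effect.** With patient variance 0.5 and 73/17 = 4.3 mentees per mentor, mentor averages vary by roughly 0.5/4.3 = 0.116, an apparent SD of 0.34. The fitted SD was 0.31, mean b was -0.054 (rate ratio 0.95), and rejections were 12.2% / 3.0% before any fallback. At 100 × 12 they were 8.2% / 3.9%, with mean b -0.037.

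**4. Fallback.** In simulations with patient heterogeneity, scaling the standard error by the Pearson dispersion cut rejections from 13-19% to about 1-2%, but b stayed shifted. A quasi-Poisson model fitted without the mentor term targets the mean ratio and would remove the shift.

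**5. Other codings (100 × 12, equal means).**
- One level per usual-care patient, shared variance (500 runs): 5.8% / 3.4% at s = 0.3 without patient variance. With patient variance 0.5 and no mentor effect, 0.0% / 3.4% and mean b +0.107, so the lean reverses.
- One shared no-mentor level: this level coincides with the control arm, so SE is about sqrt(2/324 + s²(1 + 1/17)). At s = 0.5 that is 0.52, and significance needs a rate ratio below exp(-1.96 × 0.52) = 0.36. Simulated rejections were 0% / 0% (200 runs).

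**6. Marginal alternative on the same simulated data.** Mean-rate ratio, mentor-clustered robust variance, t with J - 1 df: total rejection 3.2% to 5.7% in every setting; 1.5-3.1% / 1.5-2.5% up to s = 0.3, and 3.3-4.0% / 1.7-2.0% at s = 0.5.

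**The case against.** The strongest reply is that the mentees-only coding is an inference. The plan says random intercepts, which software normally applies to every patient, and codings that give usual-care patients a level are equally open. This stands: the firm finding is that the coding is unstated. It does not rescue the test, because no coding open under the text reliably tests equal counts at 5% when mentors or patients vary.

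Second, a conditional rate ratio is a legitimate estimand, and Section 9.1 does not say marginal or conditional. That is fair in general. Here, though, no mentor has patients in both arms, so a mentees-only coefficient is not a within-mentor contrast. It sets a median mentor against the usual-care mean.

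Third, patient variance of 0.5 at 0.27 × 12 = 3.24 expected events gives a variance-to-mean ratio of 1 + 3.24 × 0.5 = 2.6, which the planned residual check should detect. This also stands. The unscaled rejection rates in step 3 are therefore not the operating characteristics of the written plan. The shift in the estimate remains if the mentor term is kept.

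Fourth, the simulations omit the facility intercept and site adjustment. The facility factor is common to both arms and cancels from the ratio, so it does not create the shift, but the percentages are approximate.

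A reader might go further and infer that false positives fall almost entirely on the intervention's side, or that a positive result would be an artefact of the model. The documents do not support that. They fix neither the coding nor the mentor SD. A benefit share near 95% needs an SD of about 0.4 or more, and with no mentor or patient variance there is no lean.

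**Conclusion.** The concern holds in a limited form. The plan leaves open how usual-care patients enter the mentor term, and the answer changes what the primary test tests. On the natural reading, equal counts mean b = -s²/2, and the estimate leans toward the intervention whenever the fitted mentor variance is above zero. That part is algebra.

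The size is conditional. Under assumed mentor SDs of 0.3 and 0.5, the null rate ratio is about 0.96 and 0.88, and total false positives are about 7% and 14-18%. The benefit share is roughly 75-90% at 0.3 and about 95% only from 0.4. Patient heterogeneity adds to the shift; whether it adds false positives depends on how the fallback is applied. A sandwich variance alone does not move the coefficient. This should be corrected before the primary analysis, but it does not show that the trial is biased in a known direction.

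**What to change.** In Section 9.4.2 and Table 4, make the primary test the marginal (population-averaged) rate ratio from a log-link count model with the log follow-up offset and site. Treat each mentor's mentees as one cluster and each usual-care patient as his or her own cluster. Use a small-sample-corrected robust variance and a t reference.

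If the mixed model is kept, state how usual-care patients enter the mentor term, and report and test the rate ratio standardised over the mentor distribution. With a mentees-only intercept that is exp(b + s²/2), not exp(b). State also whether the quasi-Poisson fallback keeps the mentor term.

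The cost is SAP wording and a few lines of code, with no new data. The downside is a somewhat wider confidence interval, and with about 17 mentors the small-sample correction is needed. At a mentor SD of 0.5 a mild imbalance remains (3.3-4.0% for benefit, 1.7-2.0% for harm).

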#### 9.4.3 ANALYSIS OF THE SECONDARY ENDPOINT(S)

The primary evaluation will be at the end of the study period (12 to 18-months) using all available data regardless of the period end for participants, and comparisons at 3M will be secondary. For the primary evaluation, we will test the longitudinal effect of a peer mentor led telephone intervention on mentee self-management skills including 1) dialysis adherence (mean number of outpatient dialysis hours per month), 2) mean monthly inter-dialytic weight gain (IDWG), and 3) mean monthly albumin levels. We

will compare the rate of change over time of the monthly secondary endpoints between two intervention groups using linear mixed effects regression model. In the regression model, the secondary endpoint (e.g. monthly mean dialysis hours) is the outcome variable with two main effects (the intervention assignment and months from baseline) and the interaction term between the main effects. The interaction term (i.e. the difference in slopes between two groups) is the primary predictor of interest. There will be three random intercepts to account for mentor effect, facility effect (out of seven facilities) and subject effect (to account for within correlation from repeated measurements). We will evaluate differences in baseline variables identified in Table 6 and if they are different between the groups, we will adjust for them as confounders.

For the secondary evaluation at 3M, we will perform Wilcoxon rank-sum test to compare the 3-months change of secondary endpoints between the intervention mentee and control mentees. To account for confounders, we will also fit linear regression model with two random intercepts. In the regression model, the 3 months-change of secondary endpoint is the outcome variable and the intervention assignment of the mentees is the primary binary predictor. The random intercepts will account for the correlation between mentees who share a common mentor as well as the correlation between mentees who are from a common dialysis facility.

Below, each endpoint is described including its source, scoring and planned analysis approach. Additional details for scoring of surveys is provided in the PEER HD Survey Scoring guide document. Within group (mentors) for change in outcomes over time will also be evaluated.

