#### 9.4.5 BASELINE DESCRIPTIVE STATISTICS

All baseline variables will be summarized by treatment group using descriptive statistics (sample size, mean, standard deviation, median, minimum, and maximum) for continuous variables and by the number and percentage of patients for categorical variables. We will test the success of randomization by examining differences in the two treatment groups by performing two-sample Mann-Whitney non-parametric test for continuous variables, and chi-square test for the categorical variables.

This will also include an evaluation of the degree of concordance between mentors and mentees for variables considered for pairing. This includes: sex, race/ethnicity, language, age category and schedule preferences.

---

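### The self-efficacy, social support and quality-of-life models name no baseline score, although it is collected; the primary model's adjustment rule is also left open

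*Combined protocol and SAP*

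**What the plan says.** **Survey scores.** The quality-of-life paragraph of Section 9.4.3 plans a linear regression with two random intercepts for the self-efficacy, social support and quality-of-life scores. The outcome is the score at each of several time points, and the predictor of interest is the arm indicator. No baseline score is mentioned. The intercepts are presumably those for mentor and facility described earlier in 9.4.3. Section 9.4.1 adds site: "All analyses will be adjusted for site".

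The opening of 9.4.3 gives a different form for secondary endpoints at 3 months: "the 3 months-change of secondary endpoint is the outcome variable". Section 8.1 lists these instruments for all visits, including baseline. Section 6.3 places randomisation after the baseline visit.

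**Covariates generally.** Section 9.4.1 states that "Adjustment variables will be pre-specified in the following sections". For the primary count, Section 9.4.2 then says "As a randomized controlled trial, we do not anticipate the need for covariate adjustment". It makes an exception "if evaluation of patient characteristics by group identifies a failure of randomization and imbalance in key characteristics", offers age, gender, comorbidity, race and dialysis vintage as examples, and says "they will be considered as adjustment variables in the analysis". Section 9.4.5 tests baseline differences "by performing two-sample Mann-Whitney non-parametric test for continuous variables, and chi-square test for the categorical variables". For the longitudinal secondary models, 9.4.3 points to variables in a Table 6 and says "if they are different between the groups, we will adjust for them as confounders". Table 6 is not in the text available for this review.

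**The concern.** For a questionnaire score measured before randomisation and again later, the person's own baseline score is usually the strongest available predictor of the later one. A model of the follow-up score on arm alone leaves that information unused. The monthly clinical endpoints have a subject random intercept; the survey-score model does not, so none of its named terms carries within-person information. A change score uses the baseline, but with a fixed coefficient of one, which is less efficient than estimating the coefficient whenever the correlation is below one. With both forms open at 3 months, an analyst could choose between them after seeing the data.

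For the primary model, Section 9.4.1 promises named adjustment variables and 9.4.2 supplies none beyond site. Imbalance after a valid randomisation arises by chance, so a test for it does not identify prognostic variables. It is also not stated which result would be primary if adjustment were triggered. At stake are precision and completeness of pre-specification.

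**Working it through.** **1. Survey scores**

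The documents give no score SD and no baseline-to-follow-up correlation *r*, so *r* is assumed. Baseline and follow-up variances are taken as equal (σ²), and clustering is ignored. Relative variances of the arm effect:

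- raw follow-up score: σ²
- change score: 2(1 − r)σ²
- baseline as covariate (ANCOVA): (1 − r²)σ²

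The ratio of ANCOVA to raw is therefore 1 − r². The ratio of ANCOVA to change is (1 − r²)/[2(1 − r)] = (1 + r)/2.

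| r (assumed) | Change / raw | ANCOVA / raw | ANCOVA / change |
|---|---|---|---|
| 0.3 | 1.40 | 0.91 (9% lower) | 0.65 (35% lower) |
| 0.5 | 1.00 | 0.75 (25% lower) | 0.75 (25% lower) |
| 0.7 | 0.60 | 0.51 (49% lower) | 0.85 (15% lower) |

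Which of the two planned forms is better depends on whether r is above or below 0.5. ANCOVA is better than both at every value shown.

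To express this as power, take a raw-score comparison with 80% power at two-sided 0.05. With the baseline score, power becomes Φ[(1.960 + 0.842)/√(1 − r²) − 1.960], which is 83.6%, 89.9% and 97.5% at r = 0.3, 0.5 and 0.7.

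**2. Primary count**

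The plan's own figure comes first. Section 9.2 gives 0.27 events per month, a 20% reduction (0.216), 73 per group and more than 80% power. Over 18 months the expected events are 73 × 18 × 0.27 = 354.8 and 73 × 18 × 0.216 = 283.8. The variance of the log rate ratio is 1/354.8 + 1/283.8 = 0.00634. Power is Φ(0.2231/0.0796 − 1.960) = 80.0%, so the figure reproduces, with no covariates and no overdispersion.

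To size the gain from a prior event count, use the amended 12 months and an assumed between-patient dispersion *k*, which the documents do not give. The variance is [1/(0.27 × 12) + 1/(0.216 × 12) + 2k]/73:

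- k = 0.5: 0.0232, power 31.0%
- k = 1: 0.0369, power 21.2%

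These low starting values reflect the shorter follow-up and the assumed k. They are a separate matter from this point.

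A simulation then compared quasi-Poisson models with and without log(1 + prior count). It used gamma-distributed patient rates, 73 per arm, 12 months and 4,000 trials per setting, without mentor or facility effects. Variance reductions:

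| Look-back | Patient rates | k = 0.5 | k = 1 |
|---|---|---|---|
| 1 month | stable | 5.8% | 14.6% |
| 1 month | drifting (correlation 0.7) | 1.7% | 5.6% |
| 6 months | stable | 26.1% | 44.7% |
| 6 months | drifting (correlation 0.7) | 11.2% | 18.6% |

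At k = 0 a 1-month count gives no gain (−0.8%).

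Applying the stable 1-month reductions to the formula raises power from 31.0% to 32.6% (k = 0.5) and from 21.2% to 24.1% (k = 1). Simulated power went from 30.3% to 32.3% and from 20.3% to 22.3%. The gain is about 2 to 3 points at best.

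**3. The imbalance check**

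No section states a cut-off for adjustment. If the general 0.05 level were borrowed and the five example characteristics were independent, at least one would test as imbalanced in 1 − 0.95⁵ = 22.6% of correctly randomised trials.

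**The case against.** **The survey models may already use baseline.** Naming a predictor of interest does not exclude covariates. The 3-month change analysis applies to secondary endpoints, and Section 9.1 lists self-efficacy, social support and quality of life among them. This stands in part: a reader might infer that the plan rules baseline scores out, and it does not. At 3 months baseline may enter by subtraction. But subtraction is not ANCOVA, two forms remain open at 3 months, and nothing is stated for T2.

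**Table 6 may name the covariates.** This also stands. One might infer that the secondary models have no pre-specified covariates, but the list is not in the text available, so no claim is made about its content.

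**The primary analysis is sound as written.** A reader might infer bias or an inflated type I error. The documents do not support that: the site-adjusted randomised comparison is valid without further covariates, and the exception is worded as a failure of randomisation, with adjustment only considered. The point that survives is that the list is open, no rule connects the 9.4.5 tests to adjustment, and no primary result is named if adjustment occurs.

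**A prior-use covariate is not ready to adopt.** Sections 8.1 and 5.1 define no look-back window and no count; the entry criteria are yes/no for the prior month. Some patients enter because of prior-month events, and some have had under 90 days of dialysis, so a 6-month window would include time before dialysis. The simulation models neither feature. The 6-month gains above are therefore not a promise.

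**The self-efficacy scale is named inconsistently.** The modelling paragraph uses PKDSMS; Section 8.1 and the endpoint description use PDialSMS. This is probably one instrument, and it is treated as one here.

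**Conclusion.** The point holds for the self-efficacy, social support and quality-of-life models. They name no baseline score although it is collected before randomisation, and the 3-month form is ambiguous. The cost is precision: at assumed r of 0.3 to 0.7 the variance could be 9% to 49% lower than with raw scores, or 35% to 15% lower than with change scores. The direction of the gain holds whenever baseline and follow-up scores correlate; its size rests on r and on equal variances.

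The primary-model part is secondary and concerns precision and pre-specification only. The rule should be closed, but a 1-month prior count would add about 2 to 3 power points if patient rates are stable and k is 0.5 to 1, less if rates drift, and nothing without heterogeneity.

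The point should not be extended to all secondary endpoints. The monthly clinical endpoints are compared by slopes with a subject intercept, and the knowledge, coping and communication paragraphs state no regression of their own.

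**What to change.** 1. In Section 9.4.3, include the baseline score as a covariate in the self-efficacy, social support and quality-of-life models at 3 months and at T2. Use the same form in the 3-month regression for these scores, in place of the change-score outcome. Use one name for the self-efficacy scale.
2. State how a missing baseline score is handled. Section 9.4.2 already contemplates multiple imputation of covariates.
3. In Section 9.4.2, state that the site-adjusted model is the primary analysis. State that the Section 9.4.5 comparisons are descriptive and do not select covariates. In 9.4.3, replace the adjust-if-different condition with a fixed covariate list, and supply or confirm Table 6.
4. Optionally, pre-specify a baseline ED visit and hospitalisation count in the primary model, but only if existing baseline records support one common look-back window for all participants. State the window and which source prevails, and then report the site-only estimate alongside.

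The cost is one SAP amendment, dated before outcomes are analysed by arm. Items 1 to 3 need no new data. Item 4 may need further record abstraction, and records from external health systems need the participant's permission (Section 8.1).
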